### **Assessment Points**

Data will be collected from participants at the time points indicated in Table 2. All outcome measures are self-complete with the exception of the CSRI which will be telephone administered by the research team. In order to achieve maximum data collection we will also follow-up participants who have not responded by telephone to either remind them to return the questionnaires, or offer telephone support for completion. Respondents who return incomplete questionnaires will be called to collect missing data. On completion of the six-month outcome data, patients will be sent a £10 thank you voucher for their participation in the study.

All FCP practices should currently be using the 'standardised national data collection tool' for FCP (46). This template has been developed by the Chartered Society of Physiotherapy and NHS England to fulfil the NHS mandate of new service design for data collection regarding service use, patient direction and safety issues. If practices do not currently use the template, we will install this on their system and provide support for use. Data uploaded on this template will be extracted at the end of the data collection period.

#### **Outcome Measures**

A variety of self-reported, validated outcome measures will be used to determine the relative clinical effectiveness of the service delivery models. Table 2 details the patient reported outcome measures (PROMs).

Table 2: Patient Reported Outcome Measures

Patient Reported Outcome Measure	Measurement Domain	Assessment points	
Primary Outcome Measure			
SF-36 Physical Component Summary (37)	Physical function	0, 3 and 6 months	
Sec	ondary Outcome Measures		
SF-36 Mental Component Summary (37)	Mental health	0, 3 and 6 months	
EQ5D-5L (38)	Health related quality of life	0, 3 and 6 months	
Roland-Morris Disability Questionnaire (6)	Health status for low back pain	0, 3 and 6 months (LBP patients only)	
General Practice Assessment Questionnaire (39)	Satisfaction with receptionists, appointments, opening times, communication with healthcare staff, continuity of care and enablement	0, 3 and 6 months	
Client Services Receipt Inventory (CSRI) (40)	Healthcare utilisation	0, 3 and 6 months	
Return to work (self-report of absenteeism/change of work practices due to MSKD)	Function	0, 3 and 6 months	
PREOS-PC (41)	Patient reported safety in primary care	0, 3 and 6 months	

#### Healthcare Utilisation

Healthcare records will be searched for each participant to collect attendance information, prescription, referrals and investigation data related to their MSKD. We will adopt a pragmatic approach to this process, working with each individual practice (case study) to determine the most feasible method of data collection. The probable mechanism will consist of anonymised (study ID only) download of the medical records (including professional correspondence) for the duration of study participation. These data will be used in conjunction with self-report (customised CSRI) to ensure full data capture (e.g. accessing of private physiotherapy, exercise sessions or over the counter medications). In case of discrepancy between patient report and documented information on GP records, we will default to GP records as previous research has suggested these data are more reliable that patient recall (47).

### Data analysis

The quantitative data generated in this work package will be integrated with data from the realist qualitative interviews across sites (see sub-section 7). The realist evaluation process will adhere to the recently developed RAMESES II reporting standards for realist evaluation (2) as well as quality guidelines and training materials for realist evaluation that are publicly available at www.ramesesprojects.org.

Quantitative: Summary statistics will be compiled as follows by site: (i) Recruitment/Retention: Recruitment duration (start and finish date), number of patients eligible (according to study criteria) during this time, number of eligible patients approached, number of patients agreeing to participate and then completing baseline assessment, number of patients achieving completion (with accompanying inclusion rates), and date of baseline measurements for first and last completed patient. (ii) Demographic/Diagnostic: Descriptive statistics (numbers, means, standard deviations, medians, ranges, proportions as applicable) will be tabulated for all demographic and clinical features, along with number of days from baseline assessment to 3 months and to 6 months assessment. We will retain participants who fail to complete 3-month outcome measures, but complete the 6-month primary endpoint data collection. All of these summary statistics will also be accumulated across the three service model groups and in total.

Statistical comparisons will be performed as follows: Drop-out analysis: The overall drop-out rates across each of the three service model groups will be compared using a chi-squared test. The demographic and clinical features of the three groups will be compared in order to establish possible reason(s) should a statistically significant difference be seen in drop-out rates, and to be aware of inequalities between the three groups in preparation for their comparison for outcome measures.

Primary Outcome analysis: The change in SF-36 Physical Component Score from baseline to 3 months and from baseline to 6 months will be compared between the three service models using a 1-way analysis of variance. If a significant difference is seen, post-hoc unpaired t-tests comparing each pair of service models will be performed in order to determine the superior service model(s). Further comparisons of the three service models will be undertaken in the context of stepwise linear regression modelling, incorporating the demographic and clinical features of the patients, including their baseline SF-36 Physical Component Score. Dummy variables may also be included to represent individual sites. Regression analyses will include multilevel modelling in the form of a general linear mixed model with site as a random effect.

Secondary Outcomes analysis: The change in SF-36 Mental Health Score and in EQ5D-5L Health Related Quality of Life from baseline to 3 months and from baseline to 6 months will be compared between the three service models using a 1-way analysis of variance. If a significant difference is seen, post-hoc unpaired t-tests comparing each pair of service models will be performed in order to determine the superior service model(s).

A similar analysis will be performed for the Roland-Morris Disability Questionnaire score (for LBP patients only) due to the high prevalence and consultation rates for this disorder, for the General Practice Assessment Questionnaire (7, 9-10). For each of the three service models, the proportion of off work patients at baseline who reported having returned to work at 6 months will be compared using a chi-squared test. Costs analysis: Comparisons of costs between the 3 service models will be performed using appropriate statistical tests (according to the distributions of the relevant cost variables).

Health Economics analysis: Initially, we will conduct an analysis of the practice workforce team, and secondly a patient level analysis of outcomes for the sample of MSK patients recruited to the study will be undertaken.

Analysing these datasets sequentially is consistent with the overall case study design of the proposal. The analysis of the practice workforce will compare within and between the models of care, and the extent to which physiotherapists are integrated and used in front line care services. Information will be gathered for this analysis by conducting interviews with the practice managers and taken alongside reference to routine returns to the NHS Digital workforce minimum data set. Total practice human resource costs will also be estimated from the workforce data, and the proportions attributable to physiotherapy input shall be explored. The practice workforce configurations will be analysed descriptively, and undertaken with reference to the size and structure of the practice populations; how MSK consultations are allocated between different staff members; and MSK referral rates outside the practice. The purpose of this practice analysis is to provide an overview of the workforce composition and costs, and to understand how MSK conditions are managed across the case study sites.

Whole system resource use related to the presenting MSK condition will be captured prospectively for each patient through GP records reviewed at the end of the 6 month follow up period. However, GP records will not cover all service use items of interest so a customised version of the Client Service Receipt Inventory (CSRI) (45) will gather supplementary information. In particular it will cover voluntary and informal care received, medications and devices purchased over-the-counter and utilisation of private providers or the complementary medicine sector, including out-of-pocket expenditures.

The CSRI data will be gathered by telephone interview at baseline (0 months), 3 and 6 months, and will also capture time off work or undertaking usual activities. Patient research partners will be involved in the design of the final version for this study. Participants (patients and/or carers) will be provided with a diary for recording service use on a daily basis, as an optional *aide memoire*.

The analysis of the individual patient level data will be reported as a cost-effectiveness analysis using the primary outcome, SF-36 PCS, and will also be presented as a cost utility analysis, using the data collected from the EQ-5D-5L for the elicitation of the required QALY information. Details on how costs and outcomes will be gathered and the economic analysis plan, are given above. Adjustments will have to be made for any baseline variations in patient characteristics, if these are identified during the analysis. Differences in accrued QALYs between the groups will always be estimated whilst controlling for differences in baseline EQ-5D scores. The structure and type of regression model employed will be determined by the data collected and available for analysis. Given the multi-level analysis being undertaken within this study, as detailed within the statistical plan, any differences identified between any of the service models with regard to costs and/or health outcomes will be explored by an appropriate regression analysis. The base case economic analysis will adopt a direct NHS resource use cost perspective. The sensitivity analysis will explore whether or not a broadening of the analysis to a more societal perspective through the inclusion of patient out-of-pocket expenditures and productivity effects has any impact the economic conclusions.

A cost-consequences analysis will also be conducted to enable the full range of outcomes and costs, and how these are distributed across stakeholders, to be taken into consideration.

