### Sample size

The aim of this research is to determine that FCP is not substantially worse (non-inferiority analysis) than GP based practice. For the purpose of assay sensitivity, the study is designed as a three arm design which includes usual GP care, FCP and FCPAQ. This sample size computation also accounts for the similarities of patients within each GP centre and treats each GP centre as a cluster within which patients are nested.

Based on Bishop et al (36) a non-inferiority margin of 2 units in SF-36 scale, that is the standard practice is either superior or worse no more than by 2 unit is assumed. Previous research in MSKD, such as Angst et al. (45) has estimated a minimal clinically important difference from 4 points for the SF-36v.2 PCS subscale. The standard deviation of the difference between the SF-36 score between models are assumed to be 6.5 based on Salisbury et al (7). In a one sided 0.05 significance non inferior hypothesis test, to achieve 80% power, 132 subjects are required. To account for the hierarchical nature of the design, i.e. patients are nested within GP centres, this number should be inflated by the design effect.

The design effect for a cluster size of 14 and an intra cluster correlation coefficient (ICC) of 0.0075 (29) will be 1.09, requiring a total sample size to 145 per arm. After allowing for attrition of 20%, the total subjects required per arm is increased up to 181, making the total of at least 13 GP centres per arm, and a per practice sample size of approximately n=14.

It is suggested to randomise 13 GP centres to each physio model and recruit 14 patients with MSKD within each GP centre. In our pilot study, 814 patients consulted with MSKD over 6 months (practice population ~6200). Similar studies in primary care (7, 36) report estimates of 40% of consulting patients being eligible and consenting, we are confident in recruiting the required sample, enabling comparisons between sites and models.

In the analysis, GP centres are included as a random effects in a General Linear Mixed model to account for similarity of patients within each GP centre. The sample size computation was performed using a combination of nQuery 8 and SAS version 9.4 software.

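### The primary analysis tests SF-36 PCS change at 3 and at 6 months without ranking them, although 6 months is called the primary endpoint, and visit-by-visit tests leave usable 3-month data out of the 6-month comparison

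*Protocol*

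**What the plan says.** All of this is in the Protocol, section 5.3 (Work Package 3).

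- **Data analysis, Primary Outcome analysis.** "The change in SF-36 Physical Component Score from baseline to 3 months and from baseline to 6 months will be compared" across the three service models by one-way ANOVA. The next step is "If a significant difference is seen, post-hoc unpaired t-tests comparing each pair of service models will be performed in order to determine the superior service" model or models. No significance level, order of testing or adjustment for the two visits is given. Regression with baseline PCS and patient features follows, including a mixed model whose only named random effect is site.
- **Data analysis, summary statistics.** "We will retain participants who fail to complete 3-month outcome measures, but complete the 6-month primary endpoint data collection". This is the only place that singles out a visit as primary.
- **Outcome Measures, Table 2.** The entry for the primary outcome reads "Physical function 0, 3 and 6 months", with no visit marked.
- **Sample size.** "In a one sided 0.05 significance non inferior hypothesis test, to achieve 80% power, 132 subjects are required", with "a non-inferiority margin of 2 units in SF-36 scale". One comparison is sized and no time point is named. Attrition of 20% takes the requirement to 181 per arm. This one-sided 0.05 is the only significance level in the document.

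**The concern.** The paragraph that fixes the primary analysis gives two visits equal standing, while the paragraph before it treats one of them as the endpoint. If the models differ at 3 months and not at 6, or the reverse, the protocol does not say which result answers the primary question. Either visit could lead to a statement that one service model is superior.

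The second matter is efficiency and attrition. A test of 6-month change needs a 6-month value. The protocol expressly keeps patients who miss 3 months but return 6. It says nothing about the reverse case, and no part of the stated model links a patient's two follow-up scores. Some 3-month data already collected would therefore not inform the 6-month comparison, in a study that plans for one patient in five to be lost.

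**Working it through.** **1. The plan's own sample size.** Inputs from Sample size: margin 2, SD 6.5, one-sided 0.05, power 80%, cluster size 14, ICC 0.0075, attrition 20%.

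- n = 2 × 6.5² × (1.645 + 0.842)² / 2² = 130.6, so 131 per arm by the normal approximation. The noncentral t version gives 132 (power 80.2%), the printed figure.
- Design effect = 1 + 13 × 0.0075 = 1.0975 (printed as 1.09). 132 × 1.0975 = 144.9, so 145.
- 144.87 / 0.8 = 181.1, so 181.

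The chain reproduces. It is a calculation for one comparison at one level, with nothing set aside for a second visit.

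**2. Error rate if either visit counted.** Assumptions not in the document: each ANOVA is tested at 0.05, a finding at either visit counts, and the two change scores have correlation r. If the tests were independent, the chance of at least one false overall difference is 1 - 0.95² = 9.75%. Two correlated three-group F tests were simulated under no difference (145 per arm, 40,000 runs, patients treated as independent):

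| r | At least one false difference |
|---|---|
| 0.5 | 9.2% |
| 0.7 | 8.5% |
| 0.8 | 7.8% |
| 0.9 | 7.0% |

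The simulation standard error is about √(0.08 × 0.92 / 40,000) = 0.14 percentage points. If 6 months alone is decisive, the rate for the primary claim is 5%, whatever r is.

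**3. Cost of keeping both visits as equal primary tests.** A Bonferroni split (one-sided 0.025 each) raises 131 or 132 to 166 per arm by the same formula. After the design effect this is 181 (166 × 1.09 = 180.9) to 183 (166 × 1.0975 = 182.2). After attrition it is 181 / 0.8 = 226.3, so 227, to 183 / 0.8 = 228.8, so 229, against the planned 181. At 132 per arm, power would fall from 80.4% to 70.5% (normal approximation). With one primary visit none of this is needed.

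**4. Data not used at 6 months.** Planned attrition is 0.20 × 181 ≈ 36 per arm. Between none and all of these patients could have 3-month data; the document gives no split. Suppose 80% have both visits, 10% have 3 months only and 10% have neither. Using the 3-month-only patients multiplies the variance of the 6-month mean by 1 - r² × 0.10/0.90:

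- r = 0.5: 1 - 0.25 × 0.111 = 0.972
- r = 0.7: 1 - 0.49 × 0.111 = 0.946

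That is a variance reduction of about 3-5%. The standard error is √0.972 = 0.986 to √0.946 = 0.973 of its former value, a reduction of 1.4% to about 2.8%. At r = 0.9 the same formula gives 1 - 0.81 × 0.111 = 0.910.

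**The case against.** The strongest reply is that the primary time point is stated. Data analysis names 6 months, so the 3-month test can be read as supportive, and the primary claim then carries no inflation. That is a fair reading, and it is why the 7-9% is conditional. It does not settle the matter, because the paragraph that defines the primary analysis does not adopt it and Table 2 does not mark it.

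Three stronger readings are tempting, and the document supports none of them.

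- **That both visits are tested at full alpha as co-primary endpoints.** No significance level is given for the ANOVAs, and no rule says that a difference at either visit is enough.
- **That the plan is a complete-case analysis.** The protocol fixes no missing-data method. That a 6-month ANOVA needs a 6-month value follows from the test named, but imputation or sensitivity analyses may be in a statistical analysis plan that is not shown, and their absence here is no fault.
- **That attrition would bias the result by a known amount.** With 15% and 25% dropout in two models, and dropouts 3 points worse, the bias in completers would be (0.25 - 0.15) × 3 = 0.3 points, or 15% of the 2-point margin. Both inputs are invented. The 0.3 is also the total bias, not what a better model would remove: a repeated-measures model recovers only the part predicted by observed scores, and draws on 3-month scores only from dropouts who have them.

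The protocol also has safeguards that limit the concern. Non-responders are telephoned and missing items collected by phone, dropout is compared across models, and the planned regression includes baseline PCS and patient features. Dropout that depends on those covariates is largely dealt with; dropout that follows a poor or good 3-month score is not. The stated sample size already allows for 20% attrition, so unused data do not make it wrong.

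Finally, a baseline-adjusted mixed model at 6 months alone would be a defensible analysis. The repeated-measures model is better, not the only valid choice.

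**Conclusion.** The point holds in a limited form. The protocol names 6 months as the primary endpoint in one paragraph and tests 3 and 6 months on equal terms in the next. The size is an error rate of about 7-9% in place of 5%, but only if either visit counts, each is tested at 0.05 and the between-visit correlation lies between 0.5 and 0.9, all of which are assumed. If 6 months governs, there is no inflation.

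The unused 3-month data cost a modest amount of precision: about 3-5% of the variance of the 6-month mean if 10% of patients have 3-month data only and the correlation is 0.5-0.7, again assumed. Some attrition bias that observed scores could explain would also be left in, by an amount that cannot be worked out from the document. The separate question of ANOVA in a study sized for non-inferiority is not counted here. This is a cheap improvement, not an error that undermines the design.

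**What to change.** In Primary Outcome analysis, state that the 6-month PCS contrast between service models is the single primary comparison and that the 3-month contrast is secondary. Mark 6 months as primary in Table 2.

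Estimate both contrasts from one linear mixed model fitted to both follow-up visits, with baseline PCS, visit, service model, service model by visit, a random intercept for practice, and correlation between a patient's two scores. The primary result is the 6-month contrast from this model. Every patient with baseline PCS and at least one follow-up score then contributes.

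The cost is small: no new data, and the sample size stays at 132, 145 and 181 per arm. It is slightly more than a wording change, because the repeated-measures model takes the place of the visit-specific ANOVAs as the main analysis. It also relies on data being missing at random given the scores and covariates in the model, which should be stated.

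### The study is sized for non-inferiority of FCP to usual GP care, but the stated primary analysis tests for any difference and ties no result to the 2-unit margin

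*Protocol*

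**What the plan says.** In section 5.3 of the protocol, Sample size opens with the objective: "The aim of this research is to determine that FCP is not substantially worse (non-inferiority analysis) than GP based practice". It then sets "a non-inferiority margin of 2 units in SF-36 scale" and derives the base number: "In a one sided 0.05 significance non inferior hypothesis test, to achieve 80% power, 132 subjects are required". That number is inflated for clustering to 145 per arm and for 20% attrition to 181 per arm.

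Under Data analysis, the Primary Outcome analysis compares change in SF-36 Physical Component Score (PCS), to 3 months and to 6 months, across the three models by one-way ANOVA. Pairwise testing depends on a significant ANOVA, after which "post-hoc unpaired t-tests comparing each pair of service models will be performed in order to determine the superior service model(s". Further comparisons follow by stepwise linear regression and by a general linear mixed model with site as a random effect. Sample size also mentions a mixed model, to allow for similarity of patients within a practice.

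The margin, a one-sided test, a confidence bound and a non-inferiority conclusion do not appear anywhere under Data analysis.

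**The concern.** The two sections address different hypotheses. A non-inferiority test has as its null that FCP is worse by 2 units or more, and rejecting it supports the stated aim. The ANOVA has as its null that all three means are equal. Failing to reject that null says nothing about whether a 2-unit deficit has been excluded.

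The protocol states its primary analysis explicitly, so this is a contradiction within one document and not a detail left for a later plan. The answer to the declared aim depends on it, and the protocol intends the results to feed a commissioning pack. Followed literally, the study could finish with no pre-stated basis for saying that FCP is, or is not, acceptably close to GP care.

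**Working it through.** **Inputs from Sample size.** Margin 2; one-sided alpha 0.05; power 80%; SD 6.5 ("between models are assumed to be 6.5"); 13 practices per arm with 14 patients each; attrition 20%; and "The design effect for a cluster size of 14 and an intra cluster correlation coefficient (ICC) of 0.0075 (29) will be 1.09". No true difference is stated, so I assume 0.

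**Step 1: reproduce the plan's figure.**
- Normal approximation: n per arm = 2 × (1.645 + 0.842)² × 6.5² / 2² = 130.7, so 131.
- With the non-central t distribution, power is 79.9% at 131 and 80.2% at 132. The 132 is therefore a per-arm non-inferiority number.
- Design effect: 1 + 13 × 0.0075 = 1.0975 (printed as 1.09). 132 × 1.0975 = 144.9, so 145.
- Attrition: 145 / 0.8 = 181.25, stated as 181.

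A two-sided 5% test for a 2-point difference would need 2 × (1.960 + 0.842)² × 6.5² / 2² = 165.9, so 166 per arm before clustering. The 132/145/181 chain thus belongs to the one-sided 5% non-inferiority test.

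**Step 2: behaviour of the stated ANOVA.** Power comes from the non-central F distribution with 2 and 3n − 3 degrees of freedom and λ = n × Σ(μᵢ − μ̄)² / 6.5². I use n = 132 (effective number after clustering) and n = 145.6 (13 × 14 × 0.8 completers, clustering ignored, as the ANOVA does).

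Example: GP 0, FCP −2, FCPAQ 0, n = 132. The mean is −0.667, the sum of squares is 2.667, and λ = 132 × 2.667 / 42.25 = 8.33. The ANOVA is non-significant with probability 26.7%.

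| True mean relative to GP care | Non-significant, n = 145.6 | Non-significant, n = 132 |
|---|---|---|
| FCP 0, FCPAQ 0 | 95% | 95% |
| FCP −1, FCPAQ 0 or −1 | 75% | 77% |
| FCP −2, FCPAQ 0 or −2 | 22% | 27% |
| FCP −2, FCPAQ −1 | 36% | 40% |
| FCP −2, FCPAQ +1 | 4% | 6% |

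A simulation with 13 sites of 11 completers per arm and ICC 0.0075 agrees: with equal means the unclustered ANOVA is non-significant 94% of the time.

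**Step 3: behaviour of a matching test.** With 132 effective patients per arm, SE = 6.5 × √(2/132) = 0.800. The one-sided 95% bound lies 1.645 × 0.800 = 1.32 points below the estimate. In simulation that bound clears −2 in about 80% of studies when the true difference is 0, about 35% when FCP is 1 point worse, and about 5% when FCP is 2 points worse. These are the operating characteristics that Sample size promises.

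**The case against.** The strongest reply is that only the t-tests wait on the ANOVA. The regression and the mixed model carry no such condition, so a service-model coefficient and its standard error will exist whatever the ANOVA shows. This stands. A reader might infer that the study stops at a non-significant ANOVA and never estimates FCP against GP care, but the protocol does not support that. What is missing is any rule linking the estimate to the margin. The health economics text mentions a statistical plan that I have not seen. It may hold such a rule, but it would not remove the conflict in the protocol's own primary analysis.

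Second, a reader might take 22–27% as the study's actual false non-inferiority rate. The protocol nowhere says that a non-significant ANOVA will be read as non-inferiority, so the figure is conditional on that reading. It also moves with FCPAQ, from about 4% to 40% as FCPAQ runs from 1 point better to 1 point worse than GP care.

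Third, it is tempting to ask for all superiority comparisons to be deleted. The research questions in section 4.3 ask about meaningful patient benefit, and those in section 5.2 ask about improvement over usual GP care. These are legitimate questions of difference and should stay, though not as a gate.

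Two wording points are lesser. The margin sentence bounds standard practice ("the standard practice is either superior or worse no more than by 2 unit is assumed") where it should bound FCP. The opening sentence of Sample size makes the intended direction clear and the arithmetic is unaffected. The protocol also says "For the purpose of assay sensitivity, the study is designed as a three arm design which includes usual GP care, FCP and FCPAQ". It would go too far to say a third active arm can never help: if it separated from another arm, the study would have shown that it can detect a difference. But FCPAQ is a second active service, so it does not guarantee assay sensitivity.

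**Conclusion.** The mismatch is real and should be corrected before analysis. The aim set out in Sample size has no corresponding test in the protocol, and the 80% power belongs to a test that is not specified. In the assumed planning case of equal models, the ANOVA is non-significant about 95% of the time and the pairwise step is not reached, whereas a margin-based test would succeed in about 80% of such studies. Reading a non-significant ANOVA as showing FCP to be no worse would miss a full-margin deficit about 22–27% of the time when FCPAQ equals GP care or FCP, against the planned 5%.

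These figures assume SD 6.5, ICC 0.0075, about 145 analysed patients per arm, a planning difference of 0, and comparable groups. The last is uncertain, because practices are sampled by the service they already provide.

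**What to change.** In Primary Outcome analysis:

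- Define the primary comparison as FCP minus usual GP care, and separately FCPAQ minus usual GP care, in SF-36 PCS change at 6 months. Data analysis already treats 6 months as the primary endpoint.
- Estimate both from the mixed model with site as a random effect, adjusted for baseline PCS, with the covariates fixed in advance and not chosen stepwise.
- Conclude non-inferiority if the lower limit of the two-sided 90% confidence interval is above −2, and report this whatever the ANOVA shows.
- State whether the conclusion is drawn for each service separately or needs both. Power is about 80% per comparison and about 69% jointly.
- Keep difference or superiority comparisons as secondary analyses.

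In Sample size, reword the margin sentence so that it bounds how much worse FCP may be than standard practice, and drop or qualify the assay-sensitivity claim.

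The cost is wording only. The planned 181 per arm already matches this analysis, and no additional patients or data are needed.

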### 4. Aims and objectives

This project will address the lack of robust research evidence in this area by conducting a realist evaluation establishing the clinical effectiveness and costs of common FCP models of delivery.

- 4.1 Aim: To evaluate 'First Contact Physiotherapy' in general practice for patients with MSKDs, and provide evidence for the adoption of appropriate service delivery models with potential to:
  - provide optimal patient management
  - show meaningful patient benefit
  - relieve GP workload pressure
  - promote better use of healthcare resources
  - positively impact on whole systems MSK practice

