### 4.3 Research Questions:

a) What models of physiotherapy provision (FCP and non-FCP) are in operation across the UK? (WP1)

- b) Does FCP provide equitable patient management compared with usual GP care? And if so, how? (WP2-3)
- c) Does FCP show meaningful patient benefit? And if so, how and for whom? (WP2-3)
- d) Does FCP relieve GP workload pressure? Are there unintended consequences to GP workload that need to be understood? (WP2-3)
- e) Does FCP promote differences in healthcare resource usage? If so, how? (WP2-3)
- f) Does FCP positively affect whole systems MSK practice? If so, how? (WP2-3)
- g) Are there risks associated with FCP models? If so, what are they and how do they accrue? (WP2-3)

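### The superior service model is named by statistical significance alone; the plan's own 2-point margin and 4-point MCID for the SF-36 PCS play no part in the conclusion

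*Protocol*

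**What the plan says.** Section 4.1 lists among the aims that a model should have potential to "show meaningful patient benefit", and section 4.3 asks: "Does FCP show meaningful patient benefit? And if so, how and for whom".

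The Sample size part of section 5.3 states the purpose of the comparison: "The aim of this research is to determine that FCP is not substantially worse (non-inferiority analysis) than GP based practice". It then gives two reference values on the PCS. One is "a non-inferiority margin of 2 units in SF-36 scale". The other comes from earlier research, which "has estimated a minimal clinically important difference from 4 points for the SF-36v.2 PCS subscale".

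Under Data analysis, the change in PCS from baseline to 3 and to 6 months is compared across the three models by one-way ANOVA. If that is significant, "post-hoc unpaired t-tests comparing each pair of service models will be performed in order to determine the superior service model(s". The SF-36 mental health and EQ-5D-5L scores get the same two-step rule. Regression follows, including a general linear mixed model with site as a random effect.

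Neither the margin nor the MCID reappears in Data analysis, in the health economics text or in Final data synthesis.

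**The concern.** The protocol states what the pairwise t-tests are for: to pick out the superior model. No size of difference and no confidence interval is attached to that step. A model can therefore be named superior on an observed difference smaller than the margin and less than half the quoted MCID. The rule also gives no way to reach the non-inferiority conclusion for which the study was sized, and no reference point for judging whether a PCS difference is meaningful.

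The results feed an evidence-informed commissioning pack (section 1). A commissioner who reads that one model is superior is likely to take it as a reason to buy that model.

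**Working it through.** **Inputs** (section 5.3, Sample size): margin 2; SD 6.5; one-sided 5%; power 80%; cluster size 14; ICC 0.0075; attrition 20%. The protocol gives no significance level for the ANOVA or the t-tests. I assume two-sided 5%, unadjusted.

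**1. The plan's own figures.** "In a one sided 0.05 significance non inferior hypothesis test, to achieve 80% power, 132 subjects are required". The normal approximation gives 2 × 6.5² × (1.645 + 0.842)² / 2² ≈ 131 per arm. With the t distribution, power first exceeds 80% at 132 (0.802). The design effect is 1 + 13 × 0.0075 = 1.0975, and 132 × 1.0975 = 144.9, so 145. Then 145 / 0.8 = 181.25, stated as 181. The chain reproduces.

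**2. Smallest observed difference that passes the pairwise t-test.** SE = 6.5 × √(2/145) = 0.763. With a critical t of 1.968, the threshold is 1.968 × 0.763 = 1.50 points. Multiplying by √1.0975 for clustering gives 1.57.

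**3. Adding the ANOVA step.** The F test must be significant first. The smallest difference between the extreme arms for which it is:

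| Position of the third arm | Without design effect | × √1.0975 |
|---|---|---|
| Equal to one of the other two | 1.62 | 1.70 |
| Midway between them | 1.88 | 1.96 |

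So the working threshold is about 1.6 to 2.0 points, always below half of 4.

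**4. How often the label is earned.** I simulated the stated rule with 145 per arm, SD 6.5, and one model truly better than two equal ones:

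| True difference | Chance of being named superior to usual care |
|---|---|
| 1.0 | 18% |
| 1.5 | 41 to 42% |
| 2.0 | 69% |

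The last row is at the margin, not inside it. In about 99% or more of these claims the observed difference is below 4 points, which is to be expected when the true difference is at most 2.

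**5. Can one result be both non-inferior and significantly worse?** Non-inferiority at one-sided 5% needs an observed deficit below 2 − 1.650 × 0.763 = 0.74 points (0.68 with the design effect). A significant deficit needs at least 1.50 (1.57). The two regions do not overlap. They would begin to do so at about 276 completers per arm.

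**6. Sensitivity to the SD.** At 145 per arm the t-test threshold is 1.85 for SD 8, 2.08 for SD 9 and 2.31 for SD 10. It lies below the 2-unit margin at the plan's SD but not from about SD 9 upwards. It stays below 4 throughout.

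**The case against.** The margin belongs to a confidence bound, not to a point estimate. A model observed to be 1.5 points worse has an upper one-sided bound on its deficit of 1.50 + 1.26 = 2.76 and fails non-inferiority, so the protocol does not treat that result as unimportant. This is right. It rules out a stronger reading that a reader might infer: that the same result could be formally non-inferior and significantly inferior. Step 5 shows that this cannot happen at the planned size.

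Calling a significant pairwise difference superior is conventional, and interval reporting or MCID interpretation is often left to a SAP. A missing detail of that kind would be no finding. But the protocol itself states that the tests are there to determine the superior model, and a SAP written to follow it would inherit that rule.

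The question on meaningful benefit is also addressed through the mixed-methods synthesis, the cost-effectiveness analysis on PCS, QALYs and a cost-consequences analysis. This stands too: it would be too strong to say that a p-value alone answers the question. Still, none of those parts sets the PCS difference against either reference value.

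Finally, making superiority depend on reaching 4 points, or adding a table of patients who improve by 4 points, is a matter of preference. The protocol does not say whether its quoted MCID refers to differences between groups or to change within a patient.

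**Conclusion.** The concern holds in a limited form. The protocol fixes a significance-only rule for naming a superior model and leaves its own margin and MCID unused. At its planning values the label is available from an observed 1.50 points on the t-test, or about 1.6 to 2.0 points with the ANOVA step and design effect. A true difference of 1.5 points earns it about 41 to 42% of the time.

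These figures rest on 145 completers per arm, SD 6.5 and an assumed two-sided 5% level. The comparison with the 2-unit margin depends on the SD; the comparison with 4 points does not, over the range examined. The defect is a conclusion rule that ignores the size of the difference and its uncertainty. It is not a formal contradiction between two test results.

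**What to change.** In the primary outcome analysis, drop the use of t-tests to name a superior model. In its place:

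- Report each pairwise mean difference in PCS change, with its confidence interval, from the mixed model with site as a random effect, whatever the ANOVA result.
- Conclude that a model is not substantially worse only if the confidence bound excludes a deficit of 2 points. State the confidence level: the one-sided 5% of the sample size corresponds to a 90% two-sided interval. Using a 95% interval for this purpose would need about 166 per arm, against 132, before the design effect.
- Describe a significant difference as a statistical difference. Discuss its size and interval against the 4-point MCID before using the words meaningful patient benefit.
- Do not label differences by the point estimate alone. An observed deficit of 1.9 points has a 95% upper limit of 1.9 + 1.50 = 3.4, so calling it unimportant because it is under 2 would be wrong.

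This needs no new data and no larger sample. The price is somewhat more reporting and fewer headline claims of superiority.
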